6.2.3.2 Follow-up of Unresolved Adverse Events

Any AEs that are unresolved at follow-up are followed up by the Investigator for as long as medically indicated, but without further recording in the eCRF. AstraZeneca retains the right to request additional information for any patient with ongoing AE(s)/SAE(s) at the end of the study, if judged necessary.

6.2.3.3 Variables

The following variables will be collected for each AE:

- AE (verbatim).
- The date and time when the AE started and stopped.
- Intensity.
- Whether the AE is serious or not.
- Investigator causality rating against the study drug (yes or no).
- Action taken with regard to study drug.
- AE caused patient's withdrawal from study (yes or no).
- Outcome.

In addition, the following variables will be collected for SAEs:

- Date AE met criteria for a serious AE.
- Date Investigator became aware of the SAE.
- AE is serious due to.
- Date of hospitalisation (if applicable).
- Date of discharge (if applicable).
- Probable cause of death (if applicable).
- Date of death (if applicable).
- Autopsy performed (if applicable).
- Causality assessment in relation to Study procedure(s).
- Causality assessment in relation to other medication (eg, concomitant medication, background therapy).
- Description of SAE.

The intensity of the reported AEs will be assessed according to the following scale:

- Mild (awareness of sign or symptom, but easily tolerated).
- Moderate (discomfort sufficient to cause interference with normal activities).
- Severe (incapacitating, with inability to perform normal activities).

It is important to distinguish between serious and severe AEs. Severity is a measure of intensity whereas seriousness is defined by the criteria in Section 6.2.2. An AE of severe intensity need not necessarily be considered serious. For example, nausea that persists for several hours may be considered severe nausea, but not a SAE unless it meets the criteria shown in Section 6.2.2. On the other hand, a stroke that results in only a limited degree of disability may be considered a mild stroke but would be a SAE when it satisfies the criteria shown in Section 6.2.2.

6.2.3.4 Causality Collection

The Investigator will assess causal relationship between the study treatment and each AE, and answer 'yes' or 'no' to the question 'Do you consider that there is a reasonable possibility that the event may have been caused by the investigational product?'

For SAEs the causal relationship will also be assessed for other medication and study procedures. Note that for SAEs that could be associated with any study procedure the causal relationship is implied as 'yes'.

A guide to the interpretation of the causality question is found in Section 11.1.

6.2.3.5 Adverse Events Based on Signs and Symptoms

All AEs spontaneously reported by the patient or reported in response to the open question from the study personnel: 'Have you had any health problems since the previous visit/you were last asked?', or revealed by observation will be collected and recorded in the eCRF. When collecting AEs, the recording of diagnoses is preferred (when possible) to recording a list of signs and symptoms. However, if a diagnosis is known and there are other signs or symptoms that are not generally part of the diagnosis, the diagnosis and each sign or symptom will be recorded separately.

6.2.3.6 Adverse Events Based on Examinations and Tests

The results from protocol-mandated laboratory tests and vital signs will be summarised in the CSR. Deterioration as compared to Baseline in protocol-mandated laboratory values, or vital signs should therefore only be reported as AEs if they fulfil any of the SAE criteria or are the reason for discontinuation of study treatment.

If deterioration in a laboratory value/vital sign is associated with clinical signs and symptoms, the sign or symptom will be reported as an AE and the associated laboratory result/vital sign will be considered as additional information. Wherever possible the reporting Investigator uses the clinical, rather than the laboratory term (eg, anaemia versus low haemoglobin value). In the absence of clinical signs or symptoms, clinically relevant deteriorations in non-mandated parameters should be reported as AE(s).

Any new or aggravated clinically relevant abnormal medical finding at a physical examination as compared with the baseline assessment will be reported as an AE.

6.2.4 Reporting of Serious Adverse Events

All SAEs have to be reported, whether or not considered causally related to the investigational product, or to the study procedure(s). All SAEs will be recorded in the eCRF.

If any SAE occurs in the course of the study, then Investigators or other site personnel inform the appropriate AstraZeneca representatives (PAREXEL Medical services team) within one day, ie, immediately but **no later than 24 hours** of when he or she becomes aware of it.

The designated AstraZeneca representative (PAREXEL Medical services team) works with the Investigator to ensure that all the necessary information is provided to the AstraZeneca Patient Safety data entry site within 1 calendar day of initial receipt for fatal and life-threatening events and within 5 calendar days of initial receipt for all other SAEs.

For fatal or life-threatening AEs where important or relevant information is missing, active follow-up is undertaken immediately. Investigators or other site personnel inform AstraZeneca representatives (PAREXEL Medical services team) of any follow-up

information on a previously reported SAE within one calendar day, ie, immediately but **no later than 24 hours** of when he or she becomes aware of it.

Once the Investigators or other site personnel indicate an AE is serious in the eCRF, an automated email alert is sent to the designated AstraZeneca representative (PAREXEL Medical services team).

If the electronic data capture (EDC) system is not available, then the Investigator or other study site personnel reports an SAE to the appropriate AstraZeneca representative (PAREXEL Medical services team) by telephone.

The AstraZeneca representative (PAREXEL Medical services team) will advise the Investigator/study site personnel how to proceed.

The reference document for definition of expectedness/listedness is the IB for the AstraZeneca drug.

6.2.5 Laboratory Variables

Blood and urine samples for determination of clinical chemistry, haematology, and urinalysis will be taken in accordance with the Study Plan (Table 5 and Table 6) and sent to the local laboratory for analysis.

Additional safety samples may be collected if clinically indicated at the discretion of the Investigator. If local retesting occurs, the date, time of retesting and results (values, units and reference ranges) will be recorded in the appropriate section of the eCRF. Blood samples will be collected after at least 8 hr overnight fasting (except for the Screening Visit where fasting is not required).

Table 3 specifies the safety laboratory variables to be determined.

Standardised and validated laboratory reference ranges will be provided by the local laboratory performing the assessments.

Haematology/ haemostasis (whole blood):	Clinical Chemistry (serum [S] or plasma [P])
B-Haemoglobin	S-Creatinine ^a
B-Haematocrit ^a	S-Bilirubin, total
HbA1c ^b	P-Glucose ^a
	S-ALP
	S-AST
	S-ALT
Pregnancy testing	Urinalysis
Women:	Dipstick:
Urine pregnancy test ^b –for women of childbearing	U-Blood
potential (HCG minimum sensitivity of 25 IU/L), dipstick	U-Albumin
analysed at the study centre	U-Glucose
Serum β HCG (if urine pregnancy dipstick result is	Spot urine sample:
positive)	U-Albumin/U-Creatinine ^b

 Table 3:
 Laboratory Assessments

ALP=alkaline phosphatase, ALT=alanine transaminase, AST=aspartate transaminase, B=blood, HCG=human chorionic gonadotropin, S=serum, P=plasma, U=urine

a. CCI

b. These tests will be performed for verifying inclusion/exclusion criteria and not as a safety measure.

For information on how AEs based on laboratory tests should be recorded and reported, see Section 6.2.3.6.

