4.1.2 Inclusion Criteria at End of Run-in Period (Visit 3)

Patients must fulfil the following criteria in order to continue participation in the study.

- 10. Patient-specific optimal antihypertensive dose (as per Investigator's judgement) of an ARB or an ACEi for at least 6 weeks prior to Visit 4 (Day 1).
- 11. In the diabetic arm (Group 2) an appropriate stable dose of metformin or sulphonylurea, or metformin+sulphonylurea as anti-diabetic therapy for the last 12 weeks prior to Visit 4 (Day 1).
- 12. In the diabetic arm with impaired renal function (Group 1) a stable insulin dosing (intermediate, long-acting, premixed insulin, basal bolus insulin) for the last 12 weeks prior to Visit 4 (Day 1) as judged by the Investigator. Metformin or sulphonylurea, or metformin+sulphonylurea together with insulin would be accepted but is not mandatory. If used, stable dose of metformin or sulphonylurea, or metformin+sulphonylurea as anti-diabetic therapy for the last 12 weeks prior to Visit 4 (Day 1) is required.
- 13. Stable urinary sodium excretion on 2 successive 24-hr urinary sodium excretion measurements (<20% difference between Days -3 and -2).

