4.2 Exclusion Criteria

4.2.1 Exclusion Criteria at Screening Visit (Visit 1)

Patients will not be entered into this study if they meet any of the following criteria: **Study-related:**

- 1. Previous enrolment in the present study or participation in another clinical study with an investigational product during the last 6 months prior to Screening Visit (Visit 1).
- 2. Involvement in the planning and conduct of the study (applies to both AstraZeneca staff and staff at third party vendor or at the investigational sites).
- 3. Hypersensitivity to dapagliflozin, indocyanine green, sodium iodide, or iodine, or patients who have poorly tolerated indocyanine green in the past.
- 4. Pacemaker or other implanted electronic devices.

- 5. Pregnancy.
- 6. Breastfeeding.

General health-related:

- 7. Known clinically significant disease or disorder; or clinically relevant abnormal findings in physical examination, clinical chemistry, haematology, and urinalysis; or unstable or rapidly progressing renal disease; or any other condition or minor medical complaint, which, in the opinion of the Investigator, may either put the patient at risk because of participation in the study, or influence the results, or the patient's ability to participate in the study and comply with study procedures, restrictions and requirements.
- 8. Diagnosis of T1DM.
- 9. Hyperthyroidism or autonomic thyroid adenomas.
- 10. Abnormal vital signs, after 10 minutes supine rest, defined as any of the following (Visit 1):
 - Systolic blood pressure above 180 mmHg.
 - Diastolic blood pressure above 110 mmHg.
 - Pulse <50 bpm or >100 bpm
- 11. Any of the following cardiovascular/vascular diseases within 3 months prior to signing the consent at Visit 1, as assessed by the Investigator: myocardial infarction, cardiac surgery or revascularization (coronary artery bypass graft [CABG]/ percutaneous transluminal coronary angioplasty [PTCA]), unstable angina, unstable heart failure, heart failure New York Heart Association Class IV, transient ischemic attack or significant cerebrovascular disease, unstable or previously undiagnosed arrhythmia.
- 12. Patients with severe hepatic impairment (Child-Pugh C).

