4.7.3 Allocation of Patients to Treatment

Start of treatment will occur at Visit 4 (Day 1) after all Screening procedures have been performed and eligibility for the study confirmed. Patients will be enrolled to specific groups based on their diagnosis. When 17 patients have been enrolled to each specific patient group enrolment into that group will stop.

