5.2 Administration

The study consists of a 2-week, open label, Treatment Period. Patients will be provided with one bottle of dapagliflozin tablets on Day 1 (Visit 4) to last for the 14 ± 1 days of the Treatment Period.

The tablet is taken orally once daily in the morning and at approximately the same time of the day.

There are no restrictions regarding timing in relation to food. Dapagliflozin tablets contain lactose, which may cause discomfort in lactose-intolerant individuals.

The first dose of dapagliflozin will be administered at Visit 4 (Day 1) at the study site after all baseline assessments (including laboratory tests, plasma volume assessments, and bioimpedance spectroscopy measurement) have been performed.

On days of study site visits where blood sampling is scheduled, ie, Visit 5 and Visit 8, the patients will be required to bring the bottle of dapagliflozin tablets to site. At Visit 5 (Day 4), the patient will consume the tablet together with breakfast after fasting blood sampling is completed at the site. At Visit 8 (Day 14), the patient will consume the tablet together with breakfast after pre-dose bioimpedance spectroscopy measurements, pharmacokinetics blood sampling, CC

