- w. Patient will record compliance with recommended food intake, liquid intake daily in the food questionnaire. Any other food and drink consumed will also be recorded. Study treatment intake will also be recorded daily during the Treatment Period.

AstraZeneca AB
Study code: D1690C00049
Investigational product: Dapagliflozin

Clinical Study Protocol
CONFIDENTIAL

Table 6:	Study Plan with Assessments Schedule: Group 2 and Group 3 (Patients not on Insulin)
	Study I fail with Assessments Schedule, Group 2 and Group 5 (1 attents not on insum)

Study Plan	Screeni Period	ng 1	R	un-in I	Perio	d]	Freatr	nent l	Perio	d		Follow-up Period							
Visits (Clinic)	1				2	3	4			5	6		7	8				9	10			
Day	-28 to -8	-7	-6	-3	-2	-1	1	2	3	4	5	12	13 ±1d	14ª	15	16	17	18	19			
Informed consent	Х																					
Inclusion/exclusion criteria	Х					Х																
Confirm final eligibility						Xb																
Demography	Х																					
Medical and surgical history	Х																					
Vital signs ^c	Х					Х	Х			Х				Х				Х				
Physical examination	Х																	Х				
Height and weight ^d	Х						Х			Х				Х				Х				
ECG	Х																					
Briefing of patients by the study dietician regarding food boxes	Х																					
Telephone call by dietician ^e		Х																				
Dietary advice ^e			Х	Х	Х	Х	Х	Х	Х	Х	Х	Х	Х	Х	Х	Х	Х	Х				
Consumption of food from food boxes			Х	Х	Х	Х	Х	Х	Х	Х	Х	Х	Х	Х	Х	Х	Х	Х				
Blood sampling																						
For clinical chemistry and haematology ^f	Х						Х			Х				Х				Х				

AstraZeneca AB
Study code: D1690C00049
Investigational product: Dapagliflozin

Study Plan	Screeni Perioc	ng 1	R	un-in	Perio	d			J	[reatn	nent l		Follow-up Period						
Visits (Clinic)	1				2	3	4			5	6		7	8				9	10
Day	-28 to -8	-7	-6	-3	-2	-1	1	2	3	4	5	12	13 ±1d	14ª	15	16	17	18	19
							X			X				X				Х	
CCI							Х			Х				Х				Х	
Dapagliflozin PK ^h										Х				Х					
							X			X				X				Х	
CCI							X			X				X				Х	
Urinalysis																			
Spot urine sample for urinary albumin and creatinine	X																		
CCI							Х			X				Х				Х	
(Dipstick): U-albumin, U-glucose, U-blood ^j	X													X					

AstraZeneca AB
Study code: D1690C00049
Investigational product: Dapagliflozin

Study Plan	Screeni Period	ng 1	R	Run-in Period					1	reatr	nent	Follow-up Period							
Visits (Clinic)	1				2	3	4			5	6		7	8				9	10
Day	-28 to -8	-7	-6	-3	-2	-1	1	2	3	4	5	12	13 ±1d	14ª	15	16	17	18	19
						Х				Х				X			x		
CCI						X				Х				Х			Х		

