- Safety laboratory assessments (haematology and clinical chemistry)
- HbA1c
- Urine samples
- Spot urine sampling for estimation of urinary albumin excretion (UACR)
- Urine dipstick for safety laboratory assessments
- Urine pregnancy test for women of childbearing potential
- Concomitant medication
- SAEs
- Dispense equipment for 24-hr urine collection

7.2.2 Run-in Period: Day -6 to Day -1 (Patients not on Insulin) and Day -20 (at the earliest) to Day -1 (Patients on Insulin)

Patients meeting all eligibility criteria (based on available investigations) will be scheduled for the Run-in Period starting on Day -6 (patients not on insulin) or Day -20 at the earliest (patients on insulin).

- Patients will receive a phone call from the dietician on Day -7 (patients not on insulin) or Day -21 at the earliest (patients on insulin) as a reminder for the food boxes that they will have to start using from Day -6 or Day -20 (at the earliest) onwards, respectively, until the end of study; and to remind them to complete the food questionnaire starting Day -6 (patients not on insulin) or Day -20 at the earliest (patients on insulin)
- There will be regular contacts between Investigators and patients to ensure that their blood glucose is adequately controlled (by potentially adjusting/optimising their insulin doses) and to confirm that their insulin regime remains stable while on food boxes. Patient consultation with Investigator may occur at several times from Day -20 to Day -1. Exact dates will be decided on an as needed basis by patient and Investigator.
- Dietary advice and food boxes with a daily sodium content of approximately 150 mmol will start at Day -6 (patients not on insulin) or Day -20 at the earliest (patients on insulin)
- Patients will also start completing food questionnaires starting at Day -6 (patients not on insulin) or Day -20 at the earliest (patients on insulin)
- Patients will start collection of first 24-hr urine sample on Day -3

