7.2.3 Treatment Period (Day 1 to Day 14)

7.2.3.1 Visit 4: Day 1 (Dosing Initiation Visit)

Treatment with dapagliflozin 10 mg/day will be initiated on Day 1 for eligible patients after blood sampling.

- Obtain 24-hr urine sample from previous day (ie, Day -1)
- Patient to start collection of 24-hr urine sample
- Discontinue 24-hr ABPM
- Vital signs (blood pressure and pulse)
- Body weight
- Pre-dose blood and urine samples
- Safety laboratory assessments (haemoglobin, creatinine, haematocrit, and glucose all of which [except haemoglobin] are also **CC**

CCI

-

- CCI
- Patient will have breakfast at the study site along with non-study drugs
- Bioimpedance spectroscopy measurement (pre-dose; 1 hr after food intake)
- Measurements for plasma volume (pre-dose; approximately 1.5 hr after food intake)
- Administration of first dose of study drug at the study site
- Dietary advice
- Concomitant medication
- AEs/SAEs
- Review of food questionnaires completed by the patient
- Dispensation of study drug sufficient for up to 15 days of treatment duration

Patients will be asked to follow the procedures below until the next clinic visit:

- collect 24-hr urine samples on Day 2 and Day 3
- follow dietary advice daily
- complete food questionnaires daily
- **CC** for the next clinic visit on Day 4 and to bring the study drug to the clinic for consumption after the blood sampling

7.2.3.2 Visit 5: Day 4

Following procedure will be performed at this visit:

- Obtain 24-hr urine sample from previous days (ie, Days, 1, 2 and 3)
- Patient to start collection of 24-hr urine sample
- Vital signs (blood pressure and pulse)
- Body weight
- Pre-dose blood and urine samples
- Safety laboratory assessments (creatinine, haematocrit, and glucose all of which are **CC**)
- Pre-dose blood sample for dapagliflozin pharmacokinetics
- CCI
- Patient will have breakfast at the study site along with study drug (t=0) and non-study drugs
- Bioimpedance spectroscopy measurement (1 hr after study drug intake)
- Measurements for plasma volume (approximately 1.5 hr after study drug intake)
- Start 24-hr ABPM

- Verify study treatment intake from diaries
- Dietary advice
- Concomitant medication
- AEs/SAEs
- Review of food questionnaires completed by the patient

7.2.3.3 Visit 6: Day 5

Following procedure will be performed at this visit

- Obtain 24-hr urine sample from previous day (ie, Day 4)
- Discontinue 24-hr ABPM
- Verify study treatment intake from diaries
- Dietary advice

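### The pregnancy test is scheduled only at Visit 1 and Visit 8, so in Groups 2 and 3 the last scheduled result is nominally 8 to 28 days old at first dose; a Day 1 dipstick would narrow this minor gap cheaply

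*Protocol*

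**What the plan says.** The places that fix the schedule agree. In the Protocol, Tables 5 and 6 mark the pregnancy test at Screening and Day 14. The item "Urine pregnancy test for women of childbearing potential" stands in the Visit 1 list (7.2.1.1) and the Visit 8 list (7.2.3.5), and in no other visit list. The laboratory table in SAP 5.1.3.2 shows the test at Screening and end of treatment. Table 3 footnote b in Protocol 6.2.5 gives its purpose: "These tests will be performed for verifying inclusion/exclusion criteria and not as a safety measure".

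Pregnancy is exclusion criterion 5 in Protocol 4.2.1, set at Visit 1. Section 4.1.2 then introduces criteria 10 to 13 at Visit 3 with "Patients must fulfil the following criteria in order to continue participation in the study". These cover the antihypertensive dose, the antidiabetic treatment and stable sodium excretion; a negative pregnancy test is not among them. Both study plans also mark "Confirm final eligibility" on Day -1, and Section 4.7.3 starts treatment "after all Screening procedures have been performed and eligibility for the study confirmed".

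Section 1.3 says that patients having bioimpedance should not be pregnant and points to the Section 4.2 exclusions. Section 6.2.10.1 requires study drug to stop at once if a pregnancy occurs.

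**The concern.** Pregnancy status can change, or become detectable, after Visit 1. Section 4.1.2 rechecks other conditions that can change: criteria 10 to 12 repeat the Visit 1 criteria on background medication. Pregnancy gets no such repeat. With the schedule followed exactly, a pregnancy arising or becoming detectable after Visit 1 meets no scheduled test until the last dosing day. By then almost the whole course has been taken, and bioimpedance has been done twice in someone the protocol wanted to keep out of it.

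The footnote also does not fit the schedule. The other tests that carry it, HbA1c and the spot albumin:creatinine ratio, are done at Screening only, where verifying eligibility makes sense. The pregnancy test alone is repeated on Day 14, when eligibility is long settled and the result can serve only as a safety check.

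What is at stake is avoidable exposure of a pregnancy, not the validity of the efficacy analysis.

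**Working it through.** **Day count.** Protocol 3.1 makes Day -1 the day before dosing, so there is no Day 0, and Day -k to Day 1 is k days. Two figures in the plan confirm this:

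- Table 5 opens screening on Day -42. Day -42 to Day 1 is 1 + 42 - 1 = 42 days, the maximum from Visit 1 to Visit 4 in Section 7.2. Counting a Day 0 would give 43.
- 42 + 14 + 5 + 1 = 62 days, the maximum duration in Section 9.9.

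**Age of the last scheduled result at first dose, Groups 2 and 3.** Table 6 places Visit 1 on Day -28 to Day -8.

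- Earliest Visit 1: 28 days. Latest: 8 days.
- The Section 7.2.1 heading runs screening to Day -7, which would make the shortest interval 7 days. Table 6 uses that day for the dietician's call.
- If urine collection is restarted from Day -3 under Section 4.3, the result is slightly older. The protocol does not say by how much.

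**Doses before the next test.** Visit 7 is Day 13 ± 1 and Visit 8 is one day later, so Visit 8 falls on Day 13, 14 or 15. Dosing is once daily from Day 1, and the Visit 8 list puts the pregnancy test before that day's dose. Doses already taken = Visit 8 day - 1 = 12, 13 or 14. If the test were done after that day's dose, the count would be 13 to 15.

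**Procedures before the next test.** Bioimpedance and indocyanine green are scheduled on Days 1, 4, 14 and 18. The Day 1 and Day 4 sessions come before the Visit 8 test: two of each.

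**Interval between the two scheduled tests.** Nominally 8 + 13 = 21 to 28 + 13 = 41 days.

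**With a Day 1 pre-dose test.** The result is 0 days old at first dose, and 12 to 14 days remain to Visit 8. The dipstick's detection limit (25 IU/L, Table 3) still applies, so the gap is narrowed and not closed.

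**Expected number affected (assumption only).** The documents do not give the number of women of childbearing potential. If they are 0 to 20% of the 34 planned patients in Groups 2 and 3 (0 to 6.8 women), and each has a 0 to 1% chance of a pregnancy arising between Visit 1 and first dose, the expected number is 0 to 0.20 × 34 × 0.01 = 0.068. A Day 1 dipstick would detect only some of these, so the gain is smaller than this range suggests.

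**The case against.** The schedule is consistent across both documents and can be read as a deliberate choice with other safeguards. Contraception is required from consent until three months after the last dose, and an oral contraceptive alone is not accepted (4.1.1, criterion 9). Menstrual timing is estimated for premenopausal women when the urine collections are planned (6.1.1). Extra safety samples are allowed when clinically indicated (6.2.5). All of this stands, and it is why the point is minor. None of it schedules a test before the first dose.

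Two stronger readings are tempting, and neither is supported:

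- A reader might infer from the 42-day limit in Section 7.2 that the result could be 42 days old. That limit is general and matches the Day -42 start for insulin-treated Group 1. Groups 2 and 3 start no earlier than Day -28, their run-in is fixed at six days, and no text describes a two-week slip.
- A reader might infer that pregnancy is not considered at all after Visit 1. The Day -1 study-plan entries for the inclusion and exclusion criteria and for final eligibility are not limited to sodium, so the investigator can reconsider exclusion 5 there. What is missing is a fresh result.

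The cost side also has weight. A false positive on Day 1 could separate the Day -3 to -1 Baseline from dosing, in groups of 17 planned to give 15 evaluable patients. SAP Final 3.0 was amended after a dry run, and the documents do not state enrolment status, so few or no patients may remain to benefit. The documents also give no estimate of fetal risk from a two-week exposure. These are reasons to keep the change small. The mismatch between footnote b and the Day 14 test remains in any case.

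**Conclusion.** The point holds as a minor safety-schedule improvement. In Groups 2 and 3 the last scheduled pregnancy result is nominally 8 to 28 days old at first dose. Then 12 to 14 doses, two bioimpedance sessions and two indocyanine green injections precede the next test. These counts rest on the Table 6 screening window, the ±1 day window at Visit 7 and the test being done before the Visit 8 dose.

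The number of women affected is very small. The range of 0 to 0.07 rests on assumptions that the documents do not supply and shows only the order of magnitude. A reader should not infer any effect on the primary analysis: power, alpha and the endpoint windows are not touched.

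**What to change.** Add one urine pregnancy dipstick for women of childbearing potential at Visit 4 (Day 1), before dosing.

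- **Schedule.** Mark Day 1 in the pregnancy row of Table 6, and of Table 5 for consistency. In 7.2.3.1 list it under "Pre-dose blood and urine samples", to be read before bioimpedance, indocyanine green and dosing. A positive dipstick is confirmed by serum test before any of these steps.
- **Status.** State it in 5.2 or 7.2.3.1 as a condition for giving the first dose. Do not add it to the Visit 3 criteria in 4.1.2: final eligibility is confirmed on Day -1 in both tables and in the synopsis, and a Visit 4 eligibility criterion would contradict that.
- **Footnote b.** Reword Table 3 so that the Visit 1 test verifies eligibility and the Day 1 and Day 14 tests are safety checks.
- **SAP 5.1.3.2.** Mark the pregnancy test under Baseline, which SAP 5.3.18.2 defines for laboratory data as Day 1 before dosing.

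Keep the Visit 1 and Day 14 tests.

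No visit is added. Urine is already taken before dosing that day, and Section 5.2 already makes dosing wait: "The first dose of dapagliflozin will be administered at Visit 4 (Day 1) at the study site after all baseline assessments". The Day 1 24-hr urine enters neither Baseline (Days -3 to -1) nor the Days 2 to 4 average.

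The costs are one dipstick per eligible woman, a protocol amendment with whatever approvals Section 9.8 requires, and a small SAP table edit. Rarely, a patient is excluded late, after run-in. A false positive can delay dosing until the serum result arrives (turnaround not stated), and Baseline may then no longer end the day before dosing.
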